¹¹ Division of Women's Health, Department of Medicine and Department of Psychiatry, Brigham and Women's Hospital and Harvard Medical School, Boston, MA, USA.

Abstract

Background: Obesity affects more than one-third of adults in the U.S., and effective treatment options are urgently needed. Oxytocin administration induces weight loss in animal models of obesity via effects on caloric intake, energy expenditure, and fat metabolism. We study intranasal oxytocin, an investigational drug shown to reduce caloric intake in humans, as a potential novel treatment for obesity.

Methods: We report the rationale, design, methods, and biostatistical analysis plan of a randomized, double-blind, placebo-controlled clinical trial of intranasal oxytocin for weight loss (primary endpoint) in adults with obesity. Participants (aged 18–45 years) were randomly allocated (1:1) to oxytocin (four times daily over eight weeks) versus placebo. Randomization was stratified by biological sex and BMI (≥ 30 to < 35 kg/m², ≥ 35 to < 40 kg/m², ≥ 40 kg/m²). We investigate the efficacy, safety, and mechanisms of oxytocin administration in reducing body weight. Secondary endpoints include changes in resting energy expenditure, body composition, caloric intake, metabolic profile, and brain activation via functional magnetic resonance imaging in response to food images and during an impulse control task. Safety and tolerability are assessed biweekly and at a 6-week follow-up after treatment completion.

Results: Sixty-one male and female participants aged 18–45 years were randomized (mean age 34 years, mean BMI 37 kg/m²). The study sample is diverse with 38% identifying as non-White and 20% Hispanic.

Conclusion: Investigating intranasal oxytocin's efficacy, safety, and mechanisms as an anti-obesity medication will advance the search for optimal treatment strategies for obesity and its associated severe sequelae.

Keywords: Obesity; Oxytocin; Weight loss; Appetite regulation; Energy metabolism; Neuroimaging

1. Introduction

Obesity affects over 42% of the adult U.S. population [1] and is associated with increased risk of type 2 diabetes mellitus, hepatic steatosis, cardiovascular disease, cancer, and premature mortality [2]. More than 20% of U.S. health care costs are directly attributable to obesity [3]. Furthermore, obesity is a significant risk factor for severe COVID-19-associated illness, hospitalization, intensive care, and death [4]. Weight loss improves outcomes [5], but meaningful weight reduction is difficult to achieve and sustain. Available treatment options to supplement lifestyle modifications have long been limited to bariatric surgery, associated with peri-/post-operative complications [6], and weight-loss medications with modest efficacy and bothersome side effects. The established anti-obesity interventions often fail to yield sustained weight reduction, partly due to a physiological decrease in resting energy expenditure (REE) accompanying weight loss [7]. Clinical trials have revealed promising new drugs for weight management, such as the recently FDA-approved glucagon-like peptide-1 (GLP-1) receptor agonist semaglutide [8]. Nonetheless, gastrointestinal side effects are common, and most GLP-1 receptor agonists currently approved for weight loss can only be administered as subcutaneous injections [9]. There is an imperative need for novel, effective, and tolerable therapeutic strategies for weight loss to reduce obesity-associated health risks and increase the life expectancy and wellbeing of individuals with obesity.

Oxytocin is a nine amino acid peptide hormone produced by neurons in the paraventricular and supraoptic nuclei of the hypothalamus, secreted directly into brain regions involved in energy homeostasis and appetite regulation, and released into the bloodstream by the posterior pituitary gland [10–12]. Oxytocin neurons project to anorexigenic arcuate nucleus proopiomelanocortin neurons critical for regulation of energy balance, as well as the ventral tegmental area (VTA) and nucleus accumbens responsible for reward-related eating behavior. Further, oxytocin has been shown to mediate anorexigenic actions of leptin and cholecystokinin (CCK). See Figure 1 for a working model of obesity-related pathophysiology and proposed neural and metabolic oxytocin effects. Animal studies have shown that oxytocin may drive weight loss and result in sustained weight reduction by different mechanisms [13–15]. In rodents and non-human primates with diet-induced obesity, oxytocin administration prevents the physiological decrease in REE occurring with weight loss [13,16–18]. Oxytocin induces lipolysis resulting in reduced adipocyte size and decreased subcutaneous, visceral, and liver fat while preserving lean mass [13,15,17,19,20]. Exogenous oxytocin increases fat utilization [21] and might even induce conversion of white adipose tissue into thermogenic “beige” adipocytes [15]. Acute oxytocin administration reduces caloric consumption [22,23], particularly of palatable foods [24,25], whereas oxytocin antagonists have the reverse effect [26]. Further, oxytocin reduces cortisol levels and inflammation, which may, in turn, reduce caloric intake and improve metabolism [10,12].

In humans, proof-of-concept investigations show that acute intranasal oxytocin administration reduces food intake in both healthy men and women and those with obesity [21,25,27,28], potentially through modulation of neural processing in brain regions related to reward, energy homeostasis, and cognitive control [29–31]. Perturbations in these neural pathways may underly the development of obesity [32,33]. Intranasal oxytocin is well-tolerated by humans with minimal adverse events [34]. A clinical trial in a small sample of non-diabetic individuals with obesity (n=9 in the oxytocin arm) reported a significant BMI reduction after 8-week treatment with 24 international units (IU) (4 times/day) of intranasal oxytocin compared to placebo [35]. While the

findings are promising, this pilot study was small and did not assess mechanisms or safety. More extensive clinical trials are needed.

2. Methods

2.1. Study rationale, preliminary data, and aims

Given promising preclinical and preliminary clinical findings indicating beneficial effects of oxytocin on eating behavior, metabolism, and weight loss [12,35], investigation of the efficacy and safety of prolonged intranasal oxytocin administration as a potential weight-loss therapeutic in humans is warranted. Further, exploring mechanisms underlying the metabolic actions of oxytocin is of high interest. Our clinical trial addresses these key research questions by determining whether 8-week intranasal oxytocin promotes weight reduction in adults with obesity and investigating the neural and metabolic pathways leading to the proposed oxytocin effects on body weight.

We demonstrated that a single dose of 24 IU intranasal oxytocin administered to fasting men across the weight spectrum reduced caloric intake at a test meal, increased fat utilization, and improved insulin sensitivity [21]. In a crossover functional magnetic resonance imaging (fMRI) study of men with overweight or obesity, we found that 24 IU intranasal oxytocin (versus placebo) reduced brain activation to high-calorie food images in the VTA, the origin of the mesolimbic dopaminergic reward system, and other hedonic (e.g., orbitofrontal cortex [OFC] and anterior insula) and homeostatic (e.g., hypothalamus) areas [30], and reduced functional connectivity between the VTA and reward-related brain regions (e.g., amygdala and insula) [29]. In contrast, oxytocin increased activation in cognitive control-related brain regions (e.g., dorsal anterior cingulate cortex [dACC] and dorsolateral prefrontal cortex [dlPFC]) [30] and improved impulse control, as assessed using a behavioral task previously linked to eating behavior [36].

Thus, we hypothesize that 8-week intranasal oxytocin will reduce food intake (by decreasing reward-related and homeostatic drive to eat and increasing eating-related impulse control) and

body fat and weight (via effects on eating behavior, REE, and fat metabolism) with minimal side effects. We propose intranasal oxytocin as a potential novel, effective, and safe therapy for weight loss in human obesity.

Our study was designed to investigate the following:

- Aim 1 – Determine oxytocin effects on weight, REE, and body composition: We hypothesize that 8-week intranasal oxytocin compared to placebo (a) reduces body weight, (b) increases REE (adjusted for lean/fat free mass), and (c) reduces total body, visceral, and liver fat in adults with obesity.
- Aim 2 – Determine oxytocin effects on caloric intake and underlying neural pathways (fMRI): We hypothesize that intranasal oxytocin compared to placebo reduces caloric intake at a test meal (independent of weight change), mediated by (a) reduced activation (in fasted and fed states) of reward-related food motivation (VTA, OFC, anterior insula) and homeostatic (hypothalamus) brain regions during a visual food stimuli paradigm and (b) increased impulse control indicated by increased activation (fasted state) of cognitive control-related brain regions (dlPFC, dACC, anterior portion of supplementary motor cortex/preSMA) during a validated task requiring the engagement of cognitive control to suppress impulsive responses.

The study is conducted under an Investigational New Drug application cleared by the U.S. Food and Drug Administration at a single study site, and the institutional review board approved the study protocol.

2.2. Study design, participants, and randomization

We are conducting a randomized, double-blind, placebo-controlled study to investigate the effects of intranasal oxytocin (24 IU, 4 times/day, for 8 weeks) in adults with obesity (BMI ≥ 30 kg/m²), aged 18–45 years. We randomized 61 individuals to achieve our target evaluable population of at least 50 participants who complete the 8-week treatment period. Participants were stratified by

biological sex (female/male) and obesity class (class 1: BMI 30.0–34.9 kg/m², class 2: BMI 35.0–39.9 kg/m², class 3: BMI ≥40.0 kg/m²) and randomized 1:1 to receive oxytocin or placebo. The unblinded study pharmacist performed randomization. All other study staff and participants are blinded to treatment assignment. We recruited participants through Massachusetts General Hospital (MGH) and advertisements online/in the surrounding community. Table 1 summarizes the inclusion and exclusion criteria of the study.

2.3. Study and safety endpoints

The primary endpoint is percent change in body weight from baseline following 8-week intranasal oxytocin compared to placebo. Key secondary endpoints include change from baseline to end of treatment in (a) REE (adjusted for lean mass), (b) body composition (total body, visceral, and liver fat mass), and (c) caloric intake (adjusted for weight) following 8-week intranasal oxytocin compared to placebo.

Other secondary endpoints include change in metabolic profile (e.g., insulin sensitivity, lipid panel, high-sensitivity C-reactive protein [hsCRP] at 8 weeks; fat metabolism at 2 weeks), behavior (e.g., eating behavior, reward-related food motivation, impulse control, social emotional functioning, symptoms of disordered eating, depression, and anxiety), and quality of life between baseline and 8-week intranasal oxytocin treatment compared to placebo (Table 2).

We systematically assess safety and treatment tolerability throughout the study (Table 2), with a final safety visit 6 weeks after treatment completion and additional visits if needed (e.g., early termination). We categorize severity of adverse events according to the Common Terminology Criteria for Adverse Events (CTCAE, v5.0) [37] and evaluate expectedness of adverse events and relationship to study drug and procedures.

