2.5.3. Statistical analysis plan

Figure 3 shows our statistical analysis plan. We will perform statistical analyses using R statistical software, and appropriate R packages [54]. For continuous endpoints (see 2.3.), we will apply mixed model regression for repeated measurements (MMRM). We will consider the between-group (oxytocin versus placebo) difference in the least-squares mean change of each individual endpoint variable from baseline to each follow-up study time point of interest as the response in MMRM; the change from baseline to week 8 study time point (end of treatment) will be of primary interest (see 2.3.). Treatment group (oxytocin versus placebo), study time point (visit), and treatment group*study time point interaction will be included as fixed factors in MMRM. The baseline value of the endpoint variable and stratification factors (biological sex, BMI) will be entered as covariates. Additional covariates may be considered as appropriate. The intercept and time slope of individual participants will constitute random effects. Parameters of MMRM will be estimated via restricted maximum likelihood (REML). Depending on the distributional characteristics of the data, we may apply logarithmic transformations and/or robust statistical methods. We will adjust for multiple comparisons where appropriate via the approach of Hothorn, Bretz, and Westfall based on single-step simultaneous inference using a joint multivariate t-distribution [55]. We will use a modified intention-to-treat approach for efficacy analyses, including all randomized participants with available data for at least the second baseline visit

(randomization/initiation of treatment) and the first on-treatment study time point. We will apply a per-protocol approach for sensitivity analysis, including only randomized participants who complete the study and demonstrate $\geq 80\%$ adherence to treatment. We will carefully examine patterns of any missing data regarding their relationships with the outcomes of interest and incorporate uncertainty due to missing data with multiple imputations where applicable.

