We will conduct regression-based mediation analyses to explore mechanisms underlying the proposed effects of intranasal oxytocin treatment: We will investigate whether (a) the change in brain activation in key reward-related food motivation (VTA, OFC, anterior insula) and homeostatic (hypothalamus) regions during fasted and fed states as well as in cognitive control-related regions (dlPFC, dACC, preSMA) during the fasted state from baseline following 4-week oxytocin treatment mediates change in caloric intake at a test meal 6 weeks from baseline, (b) the change in caloric intake at 6 weeks from baseline mediates the percentage change in body weight at 8 weeks from baseline, and (c) the change in REE at 6 weeks from baseline mediates the percentage change in body weight at 8 weeks from baseline.

Safety and compliance endpoints (assessed at each study time point) will be reported and tested for between-group (oxytocin versus placebo) differences. Endpoints regarding the off-treatment follow-up study time point (week 14 visit) will be reported and analyzed using MMRM in relation to baseline and end of treatment (week 8 visit) time points where appropriate (separately from on-treatment analyses).

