Intranasal oxytocin may reduce body weight via multiple complementary mechanisms. Oxytocin may suppress caloric intake via reduced activation of reward and homeostatic brain regions and increased activation of cognitive control brain regions. Oxytocin reduces inflammation, which in turn may reduce appetite and increase energy expenditure. Oxytocin increases thermogenesis and energy expenditure. These effects lead to lipolysis, fat oxidation, and reduced fat mass, ultimately resulting in weight loss.

[figure not shown]

Figure 2. Study design.

Abbreviations: IU, international unit; REE, resting energy expenditure; BL, baseline visit; W, week of visit.

Order of analyses

Randomized, double-blind, placebo-controlled clinical trial

Participants: F/M, 18-45 years, BMI ≥ 30 kg/m²

Randomization at BL: 1 : 1 oxytocin : placebo

Stratification: Biological sex, BMI

1 – Endpoints

Variable	Use/Objective	Variable type	Statistical model	Methods for missing data
Change(%) in body weight (Δ_{W8-BL})	Primary endpoint	Continuous	Mixed-model regression for repeated measurements (MMRM), adjustment for multiple comparisons as appropriate via approach of Hothorn, Bretz, and Westfall	Modified intention-to-treat approach (mITT), Multiple imputation (MI) where applicable
REE (adjusted for lean mass) (Δ_{W8-BL})	Key secondary endpoint	Continuous		
Total body, visceral, and liver fat mass (Δ_{W8-BL})	Key secondary endpoint	Continuous		
Caloric intake (Δ_{W6-BL} , Δ_{W8-BL})	Key secondary endpoint	Continuous		
Metabolic profile (Δ_{W8-BL})	Secondary endpoint	Continuous		
Psychological, behavioral and quality of life assessments	Secondary endpoint	Continuous	Descriptive statistics	
Vital signs, QTc on EKG, %IBW, BMI, waist-to-hip ratio	Vital signs, EKG, anthropometrics	Continuous		
Age, biological sex, race, ethnicity, coexisting conditions, medication	Demographic and clinical variables	Continuous/Categorical		

2 – Mediators

Mediator variable	Dependent variable	Independent variable	Statistical model
Brain activation (Δ_{W4-BL}): food reward, homeostatic and cognitive control regions	Caloric intake (Δ_{W6-BL})	Treatment (oxytocin vs. placebo)	Regression-based mediation analysis
Caloric intake (Δ_{W6-BL})	Change(%) in body weight (Δ_{W8-BL})	Treatment	
REE (Δ_{W6-BL})	Change(%) in body weight (Δ_{W8-BL})	Treatment	

3 – Safety and Compliance (all study time points)

Variable	Use/Objective	Variable type	Statistical model

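### Section 2.3 adjusts the key secondary caloric-intake endpoint for an undefined weight; if weight change is meant, the comparison is no longer a purely randomized one

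*Combined protocol and SAP*

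**What the plan says.** Four places bear on how caloric intake is to be compared, and they do not define one analysis.

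- **Section 2.3** lists as a key secondary endpoint the change in "caloric intake (adjusted for weight) following 8-week intranasal oxytocin compared to placebo". It does not say whether this is baseline weight, weight at the visit, or weight change.
- **Section 2.1, Aim 2** hypothesizes that oxytocin "reduces caloric intake at a test meal (independent of weight change"). This is the only text that explains why weight enters at all.
- **Section 2.5.3** gives the covariates for all continuous endpoints: "The baseline value of the endpoint variable and stratification factors (biological sex, BMI) will be entered as covariates". It then adds: "Additional covariates may be considered as appropriate". No post-randomization weight term is named.
- **Figure 3** carries the lean-mass adjustment in the REE row but shows no weight adjustment in the caloric-intake row.

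The plan also states how it sees intake and weight to be related. In the mediation analyses of section 2.5.3, "the change in caloric intake at 6 weeks from baseline mediates the percentage change in body weight at 8 weeks from baseline". A second route to weight is posited beside it: "the change in REE at 6 weeks from baseline mediates the percentage change in body weight at 8 weeks from baseline".

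**The concern.** If the weight in section 2.3 is weight change, the model conditions on something measured after randomization that the plan expects treatment to alter and that it treats as a consequence of intake. Participants in the two arms who have the same weight change are not comparable in the way randomization makes the whole arms comparable. With a positive correlation between intake change and weight change, a real reduction in intake would be understated. If weight fell for another reason, such as REE, an apparent rise in intake could emerge where none exists.

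If the weight is baseline weight, there is no such problem. Because the plan does not say, the choice could be made after the data are seen, on a key secondary endpoint that also supports the mechanistic argument.

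**Working it through.** **Inputs.** From section 2.5.1: 25 per arm, two-sided 5% level, weight difference 3.2 kg, SD about 4 kg. The planned weight effect is therefore 3.2 / 4 = 0.8 SD. The documents give no SD, effect size or power for caloric intake and no correlation between intake change and weight change. These are assumed: a true intake effect of either 0 or a 0.8 SD reduction, and a within-arm correlation ρ of 0.3 to 0.5, with 0.7 and negative values as extensions.

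**Step 1: the plan's own figure.** 0.8 × √(25/2) = 2.83, and 2.83 − 1.96 = 0.87, which gives power of 80.7% (normal approximation). The exact t calculation with 48 df gives 79.1%. The stated 80% reproduces. It concerns body weight and is not affected by this point.

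**Step 2: what the adjusted model estimates.** Put intake change and weight change in within-arm SD units, with treatment effects δI and δW. The within-arm slope of intake on weight is then ρ, and the weight-adjusted treatment effect is

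adjusted effect = δI − ρ × δW.

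It equals δI only if ρ = 0 or δW = 0.

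**Step 3: numbers.** Estimates follow from the formula. Rejection rates come from simulation (20,000 trials per setting, 25 per arm, ANCOVA with weight change as covariate).

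| Situation | Adjusted effect, ρ = 0.3 | Adjusted effect, ρ = 0.5 | Rejection rate, ρ = 0.3 / 0.5 |
|---|---|---|---|
| δI = −0.8, δW = −0.8 | −0.8 + 0.3×0.8 = −0.56 | −0.8 + 0.5×0.8 = −0.40 | 46% / 31% (power) |
| δI = −0.8, weight changed only through intake (δW = −0.8ρ) | −0.8 + 0.3×0.24 = −0.73 | −0.8 + 0.5×0.40 = −0.60 | 74% / 64% (power) |
| δI = 0, δW = −0.8 by another route | +0.24 | +0.40 | 13% / 32% (type I error) |
| δI = 0, δW = −0.4 by another route | +0.12 | +0.20 | 6.5% / 12% (type I error) |
| δI = 0, δW = 0 | 0 | 0 | 5% / 5% (type I error) |

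Without the weight-change covariate, power is about 79% for the 0.8 SD reduction, and type I error is 4.5% to 5.2% across settings.

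Check of the first row at ρ = 0.3: variance ≈ (1 − 0.09) × (2/25 + 0.64/48) = 0.91 × 0.0933 = 0.0849, so SE ≈ 0.291 and 0.56 / 0.291 = 1.92. That lies just below the critical value of about 2.01, which agrees with power of about 46%.

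**Step 4: sensitivity.** At ρ = 0.7 the first three rows become −0.24 SD with 18% power, −0.41 SD with 47% power, and +0.56 SD with 70% type I error. A negative ρ reverses the direction: with no intake effect and δW = −0.8, ρ = −0.3 and −0.5 give −0.24 and −0.40 SD, with type I error of 12.5% and 31%.

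**The case against.** A reader might infer that the plan does adjust intake for weight change and that the key secondary comparison is therefore biased. The documents do not establish that. Section 2.3 says only weight, and Aim 2 is a hypothesis, not a model specification. The wording in section 2.3 parallels the lean-mass adjustment of REE, so scaling for body size is a possible meaning. The covariates actually named in section 2.5.3 are baseline quantities, already close to what is recommended here. Post-randomization weight could enter only through the open clause on further covariates. All of this stands, and it is why the bias is stated conditionally. It does not remove the gap: the adjustment remains undefined, and baseline weight would add little to a model that already contains BMI, so the special mention for intake still suggests something else.

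The causal direction can also be challenged. The test meal takes place at week 6 (section 2.4.6), and weight change up to that visit precedes the meal and cannot be caused by it. It may be an intermediate between treatment and meal intake, and adjusting for it would then aim at the direct effect that Aim 2 asks about. That is a fair question. Regression answers it only if prior weight change and meal intake share no unmeasured causes, such as appetite or habitual eating, and the plan states no such assumption. On this view too the comparison is not purely randomized. The simulation covers only the structure in which weight follows measured intake, so its figures do not carry over to this one.

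Finally, the larger losses need most of the weight effect to arise outside intake. At ρ = 0.3, a 0.8 SD intake effect carries only 0.3 × 0.8 = 0.24 SD of weight change, and the other 0.56 SD must come by another route. The plan posits one through REE but does not size it.

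**Conclusion.** The firm finding is an undefined and inconsistent adjustment of a key secondary endpoint: section 2.3, Aim 2, section 2.5.3 and Figure 3 do not agree. The best-supported reading of section 2.3 with Aim 2 is post-randomization weight change. On that reading the intake comparison loses its purely randomized basis.

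Whether bias follows, and how much, depends on a treatment effect on weight and a within-arm correlation between intake change and weight change. The documents give no value for the correlation. Over the assumed range of 0.3 to 0.5, a true 0.8 SD reduction could lose between about 9% (0.73 against 0.8) and half (0.40 against 0.8) of its size, depending on how weight changes. A false signal arises only if weight changes by a route other than intake. With positive correlation it points to higher intake on oxytocin, so a false benefit is not the expected error. If oxytocin affects neither variable, type I error stays at 5%. The claim that the planned analysis will show a false effect goes further than the documents allow.

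**What to change.** 1. In section 2.3, change the bracketed adjustment on caloric intake to name baseline weight, or delete it.
2. Make the key secondary intake analysis adjust only for baseline quantities: baseline intake, sex, and BMI stratum or baseline weight.
3. State the intake measure and its time point. The test meal is scheduled at baseline and week 6 only (section 2.4.6, Table 2), whereas section 2.3 refers to end of treatment and Figure 3 lists both week 6 and week 8. For the test meal, the contrast should be week 6.
4. Keep any model that adjusts for weight change as a supportive analysis for Aim 2. Label it as not a randomized comparison, say at which visit weight is taken, and state the assumption of no unmeasured common causes.
5. Align Aim 2, section 2.3, section 2.5.3 and Figure 3 accordingly.

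The cost is SAP wording and one extra model, with no new data. The downside is that the claim of an intake effect separate from weight change then rests on a supportive analysis.
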